3.2 TRIAL INVESTIGATIONS

3.2.1 Blood Tests

Screening blood samples will be taken for routine haematology and biochemistry tests including full blood count, renal function, (U&Es), liver function (LFTs), blood glucose, haemoglobin A1c, lipids, pro-NT BNP and cystatin C levels.

Routine safety bloods will be taken at visits throughout the trial: at each visit, in prescreening, baseline/randomisation, visits 3 (day 2), visits 5 (week 6) visit 6 (week9) visit 7 (week 9 + 3) and the final visit week 15.

Research bloods will be taken at randomisation visit, day 3, week 6, week 9 (post-wash out), week 9 day 3, and week 15. BNP, inflammatory markers and other markers of interest such as oxidative stress will be measured. Additional blood markers may be tested on surplus samples at a later date. The total amount of research blood taken at each visit will be no more than 20ml.

Consent will also be sought for future ethically approved genetic analysis using research blood samples. This can be declined without affecting participation in the trial. If agreement is given for this, 10ml of extra blood will be taken at the randomisation visit and anonymously stored in the Division of Molecular and Clinical Medicine, University of Dundee: any subsequent analysis of these samples will be subject to approval of a Research Ethics Committee (REC) prior to analysis.

3.2.2 Urine Tests

Participants will provide a spot urine sample for quantification of albumin/creatinine ratio and protein/creatinine ratio at 4 of the trial days. As well as four 24 hour urinary collections on the days prior to the renal physiological tests days.

3.2.3 Renal Physiological Tests

Participants will attend the Clinical Research Centre (CRC) on 4 separate trial days (2 while in each arm of the trial). On each trial day, participants will present themselves to the CRC, following an overnight fast. Two days before presenting to the CRC, participants will be required to follow a 2gm sodium and 2L fluid/day controlled diet. A 24-hour urine collection will be made in the 24 hours prior to the day of the renal physiological test. Participants will be asked to take their morning usual medications except their IMP (empagliflozin or placebo) and furosemide (or equivalent loop diuretic).

[figure not shown]
An intravenous cannula will be placed in each arm for subsequent infusion and blood sampling. Bloods will be drawn for measurement of plasma NT-proBNP (a biomarker of wall stress and will be measured as a discovery variable in this proof of concept trial) using standard protocols. Firstly, a 15 ml/kg oral water load will be administered over approximately a 15-minute period. Thereafter, at approximately 30 minute intervals, participants will be requested to void urine until the end of the trial day. The volume of urine passed will be measured and an aliquot stored for later analysis. On each occasion, the volume of urine passed will be measured, and an equal volume of water given to drink. In this way, a steady state diuresis will be established over approximately 3 hours. The last urine collection during this stabilization period will be taken as baseline. Approximately 3 hours after initiation of the test, each participant will receive an oral tablet of either empagliflozin 25mg or placebo. After the seventh urine sample, participants will be given a bolus of IV furosemide at half their total daily dose. Heart rate will be displayed continuously on an ECG oscilloscope and the blood pressure measured approximately every 60 minutes. Venous blood will be obtained at the midpoint of each clearance period for measurement of serum sodium, osmolality and creatinine. At the end of the RPT, light refreshments in the form of tea, coffee or juice with biscuits will be provided. A lunch will then be provided at the CRC.

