3 TRIAL DESIGN

3.1 TRIAL DESCRIPTION

The RECEDE-CHF Trial is a single centre randomised, double-blind, placebo-controlled, crossover, trial conducted in NHS Tayside to compare the SGLT2 inhibitor empagliflozin 25mg, to placebo. Participants will be enrolled in the trial for a period of between 14 to 16 weeks.

At the screening visit, following informed consent, an initial medical history and clinical examination will be performed and concomitant medication will be recorded. Participants will have bloods taken for safety analysis and vital signs will be checked to confirm eligibility prior to enrolment. An assessment of suitability of the trial for the potential participant will be undertaken by the principal investigator or medically qualified delegate.

Should the participant meet the inclusion criteria and have no exclusion criteria identified, they will return for the baseline/randomisation visit at the Clinical Research Centre (CRC), Ninewells Hospital, Dundee, within four weeks post screening visit. Where possible the screening visit and randomisation visits will be combined.

At the randomisation visit participants will undergo safety blood tests, vital signs and trial medication will be dispensed (either empagliflozin 25mg or placebo).

Participants will continue on trial medication, empagliflozin 25mg or placebo, once daily, for a period of 6 weeks. Participants will be educated on the symptoms of hypoglycaemia which includes a written action plan on how to manage it in the unlikely event that it occurs.

Participants will return to the CRC 3-days (±2 days) post-randomisation, for a trial day, lasting approximately 5 hours, where they will have safety and research bloods drawn, vital signs recorded and will undergo renal physiological tests (RPT). Participants will be required to provide several urine samples throughout the course of the visit.

Participants will then return again at week 6 for a trial day, lasting approximately 5 hours, where they will undergo RPT again, safety and research bloods will be drawn and vital signs recorded. Participants will be again required to provide several urine samples throughout the course of this visit. Participants will terminate trial drug, either empagliflozin 25mg or placebo, at this visit and will return to the CRC at the end of the two week wash out period (week 9)

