At week 9, participants will have safety and research bloods drawn, vital signs recorded, new trial medication dispensed, educated on the symptoms of hypoglycaemia and given a written action plan on how to manage it in the unlikely event that it occurs.

Participants will subsequently return to the CRC after 3 days (±2 days), for a trial day, lasting approximately 5 hours, where they will have safety and research bloods drawn again, vital signs recorded and will undergo renal physiological tests (RPT). Participants will be required to provide several urine samples throughout the course of the visit.

Participants will then return again at week 14 for the final trial day, lasting approximately 5 hours, where they will undergo RPT again, safety and research bloods will be drawn and vital signs recorded. Participants will be required to provide several urine samples throughout the course of the visit. Participants will terminate trial drug, either empagliflozin 25mg or placebo.

Further details of trial visits are detailed in section 7.1.

Participants not on insulin will continue with all usual medications, these remain unchanged throughout unless clinically indicated. Participants who are already on insulin at time of recruitment will be advised of the likelihood of having to reduce their total daily dose of insulin by for example by a reduction of 10% on the day they are randomised with an increase in the frequency of their blood sugar monitoring. Further dose titration will be done by the trial team, Diabetic Consultant, or GP with or without instruction from either the trial team or Diabetic Consultant, based on the participant's symptoms, home and laboratory-based blood sugar levels. Down-titration of therapy will be done in a stepwise manner starting with insulin. Other anti-diabetic agents will only be down-titrated once insulin has been discontinued. Up-titration of the IMP.

Acute exacerbations of CHF are likely to occur in the course of this trial. These will be treated as per usual practice and the empagliflozin or placebo will not need to be stopped unless the participant or their clinician specifically requests stopping or there are sound clinical reasons to do so. Anti-hyperglycaemic medications may be adjusted by the participants GP, hospital care consultant or PI as necessary during the trial; changes will be recorded in the concomitant medications.

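### On the four fasted renal test days the protocol, as written, has insulin and sulphonylurea users take those drugs before about 5 hours on water only, with no visible test-morning dosing or glucose rule

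*Protocol*

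**What the plan says.** **The test morning.** Protocol 3.2.3 has four test days, two in each arm. On each, "participants will present themselves to the CRC, following an overnight fast". The medication instruction names two exceptions only: "Participants will be asked to take their morning usual medications except their IMP (empagliflozin or placebo) and furosemide (or equivalent loop diuretic". Appendix 2 lists water as the only intake, first a load of 15 ml/kg and then replacement of each urine volume. Food comes afterwards: "At the end of the RPT, light refreshments in the form of tea, coffee or juice with biscuits will be provided", followed by lunch.

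**Background glucose-lowering drugs.** Protocol 3.1 provides for participants already on insulin. Section 6.7.1 allows everything not listed in 6.7.2, and 6.7.2 lists only the repaglinide class and thiazides. Sulphonylureas are therefore permitted by implication. For those not taking insulin: "Participants not on insulin will continue with all usual medications, these remain unchanged throughout unless clinically indicated". Section 6.6 acknowledges more hypoglycaemia when empagliflozin is given with insulin or sulphonylureas, and says that most events are mild.

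**Blood sampling.** Blood for NT-proBNP is taken around cannulation, before the water load. After that: "Venous blood will be obtained at the midpoint of each clearance period for measurement of serum sodium, osmolality and creatinine". Appendix 2 gives the timed draws as U&Es and osmolality. Glucose belongs to the safety bloods (7.2), which Appendix 1 schedules at these visits without a time.

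**General safeguards.**
- Section 3.1 gives an example 10% insulin reduction at randomisation, more frequent home monitoring and later titration.
- Sections 3.1 and 5.5.4 let the investigator, GP or clinic adjust any anti-hyperglycaemic drug when needed.
- At randomisation, "Participants will be educated on the symptoms of hypoglycaemia which includes a written action plan on how to manage it"; this is repeated at week 9.
- HbA1c below 6.0% is an exclusion (4.3), and staff ask about hypoglycaemia symptoms at visits (7.2).
- Testing is supervised with two cannulas, and "Heart rate will be displayed continuously on an ECG oscilloscope and the blood pressure measured approximately every 60 minutes".
- Study drug stops after two or more severe episodes that persist despite down-titration of other drugs (3.1).

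**The concern.** The instruction says what to withhold and, by naming two exceptions, directs that everything else be taken. For someone on a sulphonylurea or mealtime insulin, that means a glucose-lowering dose with no meal to match it, at the end of an overnight fast and before another 5 hours without food. The protocol itself identifies these drugs as the ones that raise hypoglycaemia risk alongside empagliflozin. The hazard therefore comes from a trial procedure, is foreseeable, and can be avoided at modest cost.

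Two features sharpen it. The first test in each period comes soon after study drug starts: "Participants will return to the CRC 3-days (±2 days) post-randomisation", with the same window after week 9. That leaves little time to titrate on home or laboratory readings. And for someone on both drugs, the stepwise order in 3.1 reduces insulin first and leaves other agents until insulin has been stopped.

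There is also a smaller data issue. Rescue glucose or juice during a test breaks both the fast and the volume-matched water replacement. It would disturb that day's urine volume and sodium, which SAP 9.2 analyses by repeated-measures ANOVA.

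**Working it through.** No event rate or power figure is involved. The check traces the timeline and counts exposure.

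1. **Test length.** Section 3.1 states approximately 5 hours. Appendix 2 runs from -30 min (arrival) to +270 min: 270 + 30 = 300 min = 5 h. The clock times agree: 07:30 to 12:30 in Protocol 9.1.1 and 08:30 to 13:30 in SAP section 6, both 5 h. The stated figure is reproduced.

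2. **Exposure per user who completes.** 4 tests × 5 h = 20 h of fasted testing, of which 2 × 5 h = 10 h fall in the empagliflozin period. The length of the overnight fast is not stated and is not counted.

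3. **Same-day study drug.** Appendix 2 gives the capsule at +150 min, which is 180 min after arrival. The time after it is 270 − 150 = 120 min = 2 h per test. In the empagliflozin period, 2 × 2 = 4 h follow a same-day dose and 10 − 4 = 6 h rest on dosing from previous days.

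4. **Early tests.** Day 3 ± 2 gives 3 − 2 = 1 to 3 + 2 = 5 days after study drug starts, once in each period. Two of the four tests are early, one of them on empagliflozin.

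5. **Timed draws.** They fall at +105, +135, +165, +195, +225 and +255 min: six draws, 30 min apart, none listing glucose. The first is 105 + 30 = 135 min after arrival. It is not the first blood of the day, because the NT-proBNP draw comes around cannulation. Glucose is not listed for that draw either.

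6. **Number exposed.** The documents give no share on insulin or a sulphonylurea. The possible range is 0 to 34. Protocol 1.1 describes sulphonylureas as in common use in type 2 diabetes, which makes zero unlikely but gives no figure.

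7. **Workload of the proposed checks.** 1 on arrival + 6 at the timed draws = 7 per test day; 7 × 4 = 28 per user who completes. The ceiling is 34 × 28 = 952 if all 34 were users and completed. With the planned 35% drop-out, 34 × 0.65 = 22.1, so 22 × 28 = 616 if all completers were users.

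**The case against.** The best reply is that the plan already takes hypoglycaemia seriously and that a competent team would act sensibly. Insulin is reduced, and monitored more closely, from the day of randomisation, before the first test. The investigator may adjust any anti-hyperglycaemic drug when needed, so the stepwise order does not bind and a test-morning dose could be set under the present text. Education is given before both early tests. Staff and venous access are at hand. Most events are said to be mild. All of this stands and lowers the risk. It does not answer the point: these are general or discretionary measures, none speaks to the fasted morning, and the one instruction that does points to taking the drugs. ECG and blood pressure do not measure glucose.

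A second reply is that constant background therapy protects the comparison, and that withholding it could itself change the result. This has substance and is carried into the cost of the fix.

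Third, a figure follows the quoted instruction and is not reproduced in the available text; the participant information sheet and action plan are not available either. Any of them may hold a test-day rule. The point is confined to the visible text.

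Two readings go too far. A reader might infer that glucose is measured only once per visit. Appendix 1 carries one mark per visit, but so does the renal test, which contains six draws, so a mark does not show frequency. A reader might also infer that no blood is taken for 135 minutes. The cannulation draw contradicts that, and safety bloods could be taken then, though the text does not say so.

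**Conclusion.** The point holds and should be fixed. As written, permitted insulin and sulphonylureas are taken before about 5 hours on water, with no visible rule for the dose, no timed glucose and no treatment threshold. Each user who completes faces 20 h of fasted testing: 10 h in the empagliflozin period, of which 4 h follow a same-day dose.

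This rests on three assumptions: that usual morning medicines include these drugs, that sulphonylureas are allowed because they are not prohibited, and that the unseen material holds no overriding rule. The number exposed is unknown, no event rate is claimed, and the severity of any event cannot be judged beyond the protocol's remark that most are mild.

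A reader might infer that the primary endpoint is safe from all this, or that it is compromised. Neither holds without qualification. SAP 5.4 defines the primary endpoint as the 24-hour collection at the end of treatment, which is made before the test and is unaffected. The protocol's Professional Summary instead uses urine volume in response to furosemide, and 9.1.1 powers the trial on it. That is a test-day measure, so both rescue glucose and the remedy could touch it.

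**What to change.** Amend Protocol 3.2.3 and Appendix 2 as follows.

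1. Add sulphonylureas and mealtime insulin to the medicines held until the post-test lunch that is already provided.
2. Have the investigator set, not omit, the background insulin dose for the test day. Section 6.1.6 lists ketoacidosis among empagliflozin's side effects.
3. Apply the same rule on all four test days.
4. For insulin or sulphonylurea users, do a bedside glucose on arrival, using the existing cannulation draw, and at the six existing timed draws, with a pre-set treatment threshold.
5. Record any rescue glucose as a test deviation.

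If a rule already exists in the participant information sheet or elsewhere, repeating it in these two places may be enough.

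**Cost.** Seven bedside checks per test day for users, with no extra visits or venepuncture. The amendment needs sponsor approval, then ethics, regulatory and R&D approval as applicable (Protocol 14.1). Holding the drugs may raise test-day glucose. Because empagliflozin acts by reducing renal sodium and glucose absorption, this could raise urine glucose and volume and change the test-day difference from placebo. The same rule on all four days keeps the within-participant comparison fair but does not remove that effect. The SAP's 24-hour primary endpoint is not affected.

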3.3 TRIAL FLOWCHART

Please refer to Section 7 and Appendix 1 for more detailed information regarding study specific tests being performed at each visit.

4 TRIAL POPULATION

4.1 NUMBER OF PARTICIPANTS

34 participants with underlying diabetes and well-controlled chronic heart failure (CHF) will be recruited from a range of sources as listed below in 5.1.

The PI will be responsible for recruitment but may delegate to other named individuals within the trial team. Any such delegation will be recorded on the trial delegation log and authorised by the CI.

It is anticipated it will take up to 18 months to recruit the 34 participants for randomisation with approximately 80-100 being consented into the screening trial. We anticipate a screen failure rate of 20% and a dropout rate of 35% after recruitment due to the high intensity and frequent renal physiological tests.

4.2 INCLUSION CRITERIA

Participants will be eligible if they:

- Aged 18 to 80 years with previously diagnosed Type 2 Diabetes Mellitus.
- Are diagnosed with NYHA Functional class II-III HF with prior echocardiographic evidence of LVSD.
- On stable doses of furosemide, or alternative loop diuretic for at least one month.
- Type 2 Diabetes
- eGFR ≥ 45 ml/min.
- Have stable HF symptoms for at least three months prior to consent
- On stable HF therapy for at least three months prior to consent
- Have not been hospitalised for HF for at least three months prior to consent.
- Women of childbearing potential* (WoCBP) must agree to take precautions to avoid pregnancy throughout the trial and for 4 weeks after intake of the last dose.

4.3 EXCLUSION CRITERIA

Participants will be excluded if they:

- A diagnosis of chronic liver disease and/or liver enzymes that are twice the upper limit of normal
- Systolic BP of <95mmHg at screening visit.
- HbA1c < 6.0%
- Participants on thiazide diuretics.
- Participants receiving renal dialysis
- Participants who have previously had an episode of diabetic ketoacidosis.
- Participants with type 1 diabetes mellitus
- Malignancy (receiving active treatment) or other life threatening disease.
- Pregnant or lactating women
- Participants with difficulty in micturition e.g. severe prostate enlargement
- Allergy to any SGLT2 inhibitor or lactose or galactose intolerance
- Past or current treatment with any SGLT2 inhibitor
- Participants who have participated in any other clinical interventional trial of an investigational medicinal product within 30 days.
- Participants who are unable to give informed consent
- Any other reason considered by the physician to be inappropriate for inclusion.

*Women of child bearing potential (WoCBP) are defined as premenopausal women who have not been surgically sterilised or had a hysterectomy, bilateral salpingectomy or bilateral oophorectomy. Women over 45 years old, who have not had a menstrual period for at least 12 months, without an alternative medical cause, will be considered post-menopausal.

5 PARTICIPANT SELECTION AND ENROLMENT

5.1 IDENTIFYING PARTICIPANTS

Participants will be recruited from the sources identified as:

- 1. From the HF (BIOSTAT) database in Tayside of research participants who have taken part in previous HF studies in the Department of Clinical Pharmacology, University of Dundee.
- 2. From the Diabetes and Cardiology clinics at any of the four NHS Tayside locations (Ninewells Hospital, Arbroath Royal Infirmary, Stracathro Hospital and Perth Royal Infirmary).
- 3. From SHARE, the Scottish Health Research Register, where participants have pre-consented to be invited for research.
- 4. From the Scottish Diabetes Research Network (SDRN), where patients have previously been involved in diabetes trials and have consented to being approached for future research, including those registered on the GoDARTS Database.

The PI will be responsible for recruitment but may delegate to other named individuals within the trial team. The PI or delegate may remotely screen electronic records to identify potentially suitable people and appropriate approvals will be in place to allow them to do so.

5.2 CONSENTING PARTICIPANTS

The PI, research nurse or delegate will either approach directly suitable participants at the clinical areas specified above or they will be approached indirectly by letter. Medical notes, which can be accessed via online systems such as Clinical Portal, will be reviewed to initially assess a participant's suitability. A review of the medical notes will be made to assess inclusion criteria (as listed in 4.2), and to identify if exclusion criteria (listed in 4.3) are met, prior to being approached. The letter will be sent either from their clinical consultant responsible for their care or from the CI, either directly or on his behalf by the UoD Health Informatics Centre (HIC), if required. Prior consent for contact is in place for participants registered to the research databases described above. Those registered with SHARE have also provided consent for access to and use of their electronic health records in order to identify them as potentially eligible participants for the trial.

When first contact is via letter (or telephone/e-mail if it is via SHARE, as per participant choice), a brief Participant Information Sheet (bPIS) will be sent which gives a general overview of the trial. Participants will be asked to contact the research team if they are

interested in the trial. All participants will be given at least 24 hours to consider their response and will be asked to return an expression of interest in a stamped, addressed envelope.

Should participants express an interest in taking part in the trial from the bPIS they will be provided with a full participant information sheet (PIS) by post. They will be given at least 24 hours to consider participation before they are scheduled to attend the research clinic at the CRC, Ninewells Hospital. When first contact is directly via a Clinic, potential participants will be given full PIS. All participants will be given at least 24 hours to consider participation before a screening visit is arranged by the research fellow or delegate.

Participants will have the opportunity to ask questions about the trial when the screening visit is being arranged and at the screening visit, where the informed consent discussion will take place. If they decide to participate, written informed consent will be taken and eligibility assessed by confirming all inclusion/exclusion criteria – medical notes will also be reviewed again at this stage. The CI, PI, research nurse or appropriately trained and qualified delegate will carry out informed consent.

Where a participant requests to speak with a physician from the trial team the consent process will not be completed until the participant has spoken to the physician and had all their guestions answered to their satisfaction.

Participants will be asked for their consent for a member of the Research team (CI, PI or research nurse) to inform the GP of the individual's intent to participate in this study. Those participants who do not agree to their GP being informed of participation in this study will be excluded from the study.

All individuals taking informed consent will have received training in Good Clinical Practice (GCP) and will adhere to the TASC SOP07 on informed consent. It will be explained to participants that they are under no obligation to enrol in the trial and that they can withdraw at any time during the trial, without having to give a reason. A copy of the signed informed consent form (ICF) along with a copy of the PIS will be given to the trial participant. The original signed consent form will be retained at the trial site (filed in the TMF) and one copy filed in the medical notes.

